5.4.2 Investigator-assessed DFS in Patients with PD-L1 Expression Status IC1/2/3

Investigator-assessed DFS in patients with PD-L1 expression status of IC1/2/3 is defined as a secondary endpoint. The definition of DFS is the same as that of the primary endpoint of investigator-assessed DFS. Investigator-assessed DFS in this population will be analyzed similarly to the analysis of investigator-assessed DFS in the ITT population.

5.4.3 IRF-assessed DFS

IRF-assessed DFS is defined as the time from randomization to death from any cause or the first documented recurrence assessed by IRF using the methodology in the revised IRF Charter, whichever occurs first. Data for patients without an IRF-assessed DFS event will be censored at the last date the patient was assessed to be alive and IRF-assessed recurrence free (or, for patients with no post-baseline disease assessment, at the randomization date). Patients who were determined to have baseline

disease in the 2nd Stream read will be censored at the randomization date. IRF-assessed DFS will be analyzed similarly to the analysis of investigator-assessed DFS.

5.4.3.1 Sensitivity Analyses for Impact of IRF Tumor Assessment Methodology Revision

The impact of the IRF tumor assessment methodology revision on the IRF-assessed DFS (see Section 1.2.3.1 for details) will be assessed by analyzing IRF-assessed DFS per the original charter and the concordance between the results assessed following the two charters.

The IRF-assessed DFS per the original charter is defined as the time from randomization to death from any cause or the first documented recurrence assessed by IRF per the original charter, whichever occurs first.

Data for patients without an IRF-assessed DFS event per the original charter will be censored at the last date the patient was assessed to be alive and IRF-assessed recurrence free (or, for patients with no post baseline disease assessment, at the randomization date). Patients who were determined to have baseline exclusionary lesions per protocol or meet recurrence criteria at baseline per the original charter will be censored at the randomization date.

The following analyses will be performed at the final analysis of investigator-assessed DFS:

- The IRF-assessed DFS per the original charter will be compared between treatment arms using similar analysis methods to the ones for the IRF-assessed DFS per the revised charter.
- The concordance between DFS assessed by the two IRF tumor assessment methodologies will be summarized by treatment arm (e.g., the concordance of event numbers and the concordance of IRF-assessed DFS dates between the two IRF tumor assessment methodologies).
- Additional sensitivity analyses may be conducted if deemed necessary.

5.4.4 IRF-assessed DFS in Patients with PD-L1 Expression Status IC1/2/3

IRF-assessed DFS in patients with PD-L1 expression status of IC1/2/3 is defined as a secondary endpoint. The definition of DFS is the same as that of the secondary endpoint of IRF-assessed DFS. IRF-assessed DFS in this population will be analyzed similarly to the analysis of IRF-assessed DFS in ITT population.

5.4.5 IRF-assessed EFS

IRF-assessed EFS is defined as the time from randomization to death from any cause, or the first documented recurrence in patients without baseline disease by IRF or the first documented disease progression in patients identified as having baseline disease by IRF, whichever occurs first. Data for patients without an IRF-assessed EFS event will be

censored at the last date the patient was assessed to be alive and IRF-assessed event free (or, for patients with no post-baseline disease assessment, at the randomization date). IRF-assessed EFS will be analyzed similarly to the analysis of IRF-assessed DFS.

5.4.6 Disease-specific Survival

Disease-specific survival (DSS) is defined as the time from randomization to death from RCC. Data for patients who have not died will be censored at the last date known to be alive. Data for patients who died from causes other than RCC will be censored at the date of death. Data for patients with no post baseline information will be censored at the randomization date. DSS will be analyzed similarly to the analysis of investigator-assessed DFS.

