DFS, as assessed by an independent central radiological review, will be included as a secondary endpoint. The S–TRAC study comparing sunitinib versus placebo in the adjuvant setting of RCC reported a disagreement rate between IRF-assessed and investigator-assessed DFS events of 11.3% in the sunitinib group and 8.5 % in the placebo group. Investigators called relapse earlier than the blinded independent central review more often for sunitinib than for placebo. This led to a statistically significant DFS benefit for the IRF-assessed DFS analysis but not the investigator-assessed DFS analysis (Ravaud et al. 2016). In addition, a recent Phase III trial investigating girentuximab versus placebo compared investigator assessment to independent radiologic review at baseline. Eleven percent of patients determined disease–free at baseline by the investigator were diagnosed with metastatic disease by independent radiologic review, supporting the need to confirm disease–free status by independent central radiologic review at baseline and radiographic disease recurrence throughout the trial (Chamie et al. 2016).

IRF-assessed DFS has been added as a secondary efficacy objective endpoint because retrospective IRF review may identify patients with disease at baseline, who had already been enrolled onto the study, and received study treatment. IRF-assessed DFS allows the assessment of treatment benefit in both patients with and without identified baseline disease.

OS is included as an important secondary endpoint. Because subsequent treatments after disease recurrence are evolving, the impact of adjuvant treatment on OS may be

confounded by the use of subsequent therapies. DMFS is also included as a secondary endpoint because distant recurrence is considered to be a major threat to patient survival. This endpoint will be informative as to how atezolizumab adjuvant treatment might affect patterns of recurrence. Additionally, DSS (also known as cancer-specific survival) is a secondary endpoint because non-RCC cancer mortality in this frail and elderly population can be quite significant and may be a competing cause of mortality. Comorbidities that result in death from non-RCC causes are an independent prognostic factor for OS in patients with RCC (Berger et al. 2008). Hence, improvement in DSS in this population may not be reflected in an analysis of OS.

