5.3.2 Main Analytical Approach for Primary Endpoint

The statistical hypothesis which will be tested for investigator-assessed DFS is given in Section 2. Investigator-assessed DFS will be compared between treatment arms using the stratified log-rank test. The HR for recurrence or death will be estimated using a stratified Cox proportional hazards model, and the 95% CI for the HR will be provided.

The stratified analysis will use the same factors as the randomization stratification factors. The stratification factors will be obtained from the IxRS. If there is at least one stratum with less than 20 events, the geographic region will be removed as a factor in the model given its limited prognostic significance. After removing the geographic region, if there is still at least one stratum with less than 20 events, the stratification factor that contains the level with the smallest number of patients will be removed from the stratified analysis.

Results from an unstratified analysis will also be provided.

Kaplan-Meier methodology will be used to estimate for each treatment arm the investigator-assessed DFS rate at specific timepoints (e.g., every 6 months or yearly), and to estimate median DFS; Kaplan-Meier curves will be produced. Brookmeyer-Crowley methodology ([Brookmeyer and Crowley 1982](#)) will be used to construct the 95% CI for the median DFS for each treatment arm.

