5.5 EXPLORATORY ENDPOINTS ANALYSIS

Exploratory analyses of the following primary and secondary endpoints will be performed at various timepoints (e.g., every 6 months after randomization): investigator-assessed DFS, OS, IRF-assessed DFS, IRF-assessed EFS, DSS and DMFS. Event-free rates will be estimated by Kaplan-Meier methodology, and the 95% CI will be estimated using

Greenwood's formula. The 95% CI for the difference in event-free rates between the two arms will be estimated using the normal approximation to the binomial distribution.

To assess the consistency of study results in subgroups defined by demographic and baseline characteristics, efficacy outcomes of investigator-assessed DFS, OS, IRF-assessed DFS and IRF-assessed EFS in patient subgroups will be examined. Summaries of these endpoints, including unstratified HRs estimated from the Cox proportional hazards model and Kaplan-Meier estimates of the median will be produced separately for each level of the subgroup.

Investigator-assessed DFS will be summarized in patients with tumor Fuhrman Grade 4 or sarcomatoid histology (defined by investigator-assessed conventional histopathology). The definition of DFS is the same as that of the primary endpoint of investigator-assessed DFS. Investigator-assessed in this population will be analyzed similarly to the analysis of investigator-assessed DFS in the ITT population.

Exploratory biomarker analyses will be performed in an effort to understand the association of these markers with study drug response and mechanism of action, including efficacy and/or adverse events. Biomarker analyses may be described in a separate analysis plan and summarized in a separate report.

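### Kaplan-Meier rates for disease-specific survival censor non-RCC deaths and so modestly overstate the actual risk of dying from RCC; a cumulative incidence estimate should be added

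*SAP*

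**What the plan says.** SAP 5.4.6: "Disease-specific survival (DSS) is defined as the time from randomization to death from RCC". For deaths from other causes, "Data for patients who died from causes other than RCC will be censored at the date of death". Protocol 6.4.2 has the same rule.

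On method, "DSS will be analyzed similarly to the analysis of investigator-assessed DFS". The DFS analysis in SAP 5.3.2 is a stratified log-rank test and Cox model, and in addition "Kaplan-Meier methodology will be used to estimate for each treatment arm the investigator-assessed DFS rate at specific timepoints". SAP 5.5 lists DSS by name among the endpoints with event-free rates at, for example, six-monthly timepoints: "investigator-assessed DFS, OS, IRF-assessed DFS, IRF-assessed EFS, DSS and DMFS. Event-free rates will be estimated by Kaplan-Meier methodology". Greenwood intervals and an interval for the between-arm difference accompany these rates. Protocol 6.4.3 says the same.

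Protocol 3.3.6 explains why DSS is an endpoint at all: "non-RCC cancer mortality in this frail and elderly population can be quite significant and may be a competing cause of mortality". It adds that comorbidity deaths could keep an improvement in DSS from showing in OS.

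Neither document names a cumulative incidence function or any other competing-risk method.

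**The concern.** The plan gives competing mortality as its reason for having DSS, then estimates DSS rates by a method that treats a competing death as ordinary censoring. Ordinary censoring means the patient could still have the event later, unobserved. A patient who has died of another cause cannot die of RCC. Kaplan-Meier nevertheless redistributes that patient's weight to those still at risk, so 1 minus Kaplan-Meier exceeds the proportion who actually die of RCC whenever an RCC death follows a non-RCC death in that arm.

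The absolute DSS rates and their between-arm difference are at stake, because a reader of the study report will naturally take them as real-world risks. The gap grows with follow-up. It also differs between arms, because it depends on each arm's RCC and non-RCC hazards.

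**Working it through.** **The plan's own figures.** The documents give no DSS figure, so the OS design that supplies the all-cause hazard was reproduced first. Inputs from SAP 3.2, 3.3 and Table 2: medians 100 and 143 months, looks at 190, 222 and 254 deaths, boundaries 0.036, 0.036 and 0.011, 764 patients over 33 months, 2% dropout over 24 months. Simulated power is 75.3% (stated 75%) and two-sided familywise error 0.0501 (stated 0.05). Projected deaths at Months 67, 77 and 88 are 190.9, 221.7 and 253.2 with uniform accrual, or 185.0, 216.1 and 248.0 with a linear 8-month ramp (stated 190, 222 and 254). The exponential OS assumption is therefore a fair basis.

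**Assumptions not in the documents.** Constant cause-specific hazards, and a share *s* of the all-cause hazard due to non-RCC death, taken as 20-40%.

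**Formulas.** With h = ln 2 / 100 = 0.006931 per month on placebo:

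- actual probability of RCC death by time t: CIF = (1 − s)(1 − e^(−ht))
- planned estimate: 1 − KM = 1 − e^(−(1−s)ht)

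At 36 months ht = 0.2495 and 1 − e^(−ht) = 0.2208. At 60 months ht = 0.4159 and 1 − e^(−ht) = 0.3402.

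| Months | s | CIF | 1 − KM | Excess (points) |
|---|---|---|---|---|
| 36 | 20% | 0.8 × 0.2208 = 17.7% | 1 − e^(−0.1996) = 18.1% | 0.43 |
| 36 | 40% | 0.6 × 0.2208 = 13.3% | 1 − e^(−0.1497) = 13.9% | 0.65 |
| 60 | 20% | 0.8 × 0.3402 = 27.2% | 1 − e^(−0.3327) = 28.3% | 1.08 |
| 60 | 40% | 0.6 × 0.3402 = 20.4% | 1 − e^(−0.2495) = 22.1% | 1.67 |

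On atezolizumab (median 143 months) the same shares give an excess of 0.22-0.33 points at 36 months and 0.57-0.87 at 60.

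**Between-arm difference.** Assume the same non-RCC hazard in both arms, 30% of the placebo all-cause hazard: 0.3 × 0.006931 = 0.002079. The all-cause hazard on atezolizumab is ln 2 / 143 = 0.004847. The RCC hazards are then 0.004852 (placebo) and 0.002768 (atezolizumab). At 60 months:

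- 1 − KM: 25.26% − 15.30% = 9.96 points
- CIF: 23.82% − 14.41% = 9.41 points

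At 36 months the differences are 6.54 and 6.32 points. In this scenario Kaplan-Meier enlarges the apparent absolute benefit by about 0.2 points at 36 months and 0.55 at 60, with no imbalance in non-RCC deaths.

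**The case against.** The strongest reply is that Kaplan-Meier DSS is not wrong but answers a different question. SAP 5.4.8 defines the DFS rate explicitly as a probability of being alive and recurrence-free, while nothing defines the DSS rate as the probability of dying from RCC. Protocol 3.3.6 wants RCC mortality isolated from other deaths, and censoring those deaths targets that net quantity. This stands in part: net survival is a legitimate reading. It requires independent causes of death, though, and the SAP states neither the assumption nor the interpretation.

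Second, the effect is small against sampling error. With about 382 patients per arm, the binomial standard error is √(0.160 × 0.840 / 382) = 1.9 points at 36 months and √(0.253 × 0.747 / 382) = 2.2 points at 60 (1 − KM at s = 30%). This also stands, although a systematic error in a known direction differs in kind from sampling noise.

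Third, other parts of the plan may cover the gap. SAP 5.6.2 tabulates causes of death by arm and protocol 6.4.2 promises sensitivity analyses for secondary endpoints. The tables are safety summaries, not time-based risk estimates in the ITT population. The SAP specifies no sensitivity analysis for DSS.

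A reader might also infer more than the documents support:

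- *A larger bias at 88 months.* Month 88 is calendar time from the first randomization. With 33 months of accrual, follow-up then runs from about 55 to 88 months, so almost nobody is at risk at 88 months.
- *A biased DSS median.* Even with every death counted, 1 − e^(−0.006931 × 88) = 45.7% on placebo, so no median would be reached under the design assumptions.
- *An invalid DSS comparison.* Censoring competing deaths is correct for a cause-specific log-rank test and hazard ratio.
- *A settled competing risk of known size.* The protocol says only that it may be one and gives no share of deaths.

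**Conclusion.** The concern holds as a matter of estimation and labelling. Read as absolute risk, the planned DSS rates overstate RCC mortality. The direction is certain once RCC deaths follow non-RCC deaths. The size rests on the assumed 20-40% non-RCC share, constant hazards and the design OS medians: about 0.4-0.65 points at 36 months and 1.1-1.7 points at 60 months on placebo.

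The distortion of the between-arm difference was about half a point at 60 months in the single scenario worked. If non-RCC hazards differed between arms it could be larger or change sign.

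This is a minor point. DSS lies outside the DFS-then-OS hierarchy in SAP 3.1, so type I error, power and sample size are untouched.

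**What to change.** In SAP 5.4.6, keep the stratified log-rank test and Cox hazard ratio and label both cause-specific. In SAP 5.4.6 and 5.5, take RCC-death rates and their between-arm differences from the Aalen-Johansen cumulative incidence function, with non-RCC death as a competing event. Show the cumulative incidence of non-RCC death by arm beside it. If a Kaplan-Meier DSS curve is retained, label it as net survival and state the independence assumption.

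The cost is one standard extra output. No new data are needed, because the DSS definition already requires cause of death.

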5.4.7 Distant Metastasis-free Survival

Distant metastasis-free survival (DMFS) is defined as the time from randomization to death from any cause or the date of a DMFS event, defined as diagnosis of distant (i.e., non-locoregional) metastases assessed by investigator, whichever occurs first. Data for patients without a DMFS event will be censored at the last date the patient was assessed to be alive and free of distant metastasis (or, for patients with no post-baseline disease assessment, at the randomization date). Patients who develop a local (e.g., renal bed or new tumor in ipsilateral kidney) recurrence will continue to be followed until the occurrence of a distant metastasis. DMFS will be analyzed similarly to the analysis of investigator-assessed DFS.

5.4.8 One, Two, and Three-year Investigator-assessed DFS Rate

One, two, and three-year investigator-assessed DFS rate is defined as the probability of patients being alive and free of recurrence assessed by investigator at Year 1, 2, and 3 after randomization. The DFS rates will be estimated by Kaplan-Meier methodology, and the 95% CI will be estimated using Greenwood's formula. The 95% CI for the difference in one, two, and three-year DFS rates between the two arms will be estimated using the normal approximation to the binomial distribution.

5.4.9 One, Two, and Three-year IRF-assessed DFS Rate

One, two, and three-year IRF-assessed DFS rate is defined as the probability of patients being alive and free of recurrence assessed by IRF at Year 1, 2, and 3 after randomization. One, two, and three-year IRF-assessed DFS rate will be analyzed similarly to the analysis of one, two, and three-year investigator-assessed DFS rate.

5.5 EXPLORATORY ENDPOINTS ANALYSIS

Exploratory analyses of the following primary and secondary endpoints will be performed at various timepoints (e.g., every 6 months after randomization): investigator-assessed DFS, OS, IRF-assessed DFS, IRF-assessed EFS, DSS and DMFS. Event-free rates will be estimated by Kaplan-Meier methodology, and the 95% CI will be estimated using

Greenwood's formula. The 95% CI for the difference in event-free rates between the two arms will be estimated using the normal approximation to the binomial distribution.

To assess the consistency of study results in subgroups defined by demographic and baseline characteristics, efficacy outcomes of investigator-assessed DFS, OS, IRF-assessed DFS and IRF-assessed EFS in patient subgroups will be examined. Summaries of these endpoints, including unstratified HRs estimated from the Cox proportional hazards model and Kaplan-Meier estimates of the median will be produced separately for each level of the subgroup.

Investigator-assessed DFS will be summarized in patients with tumor Fuhrman Grade 4 or sarcomatoid histology (defined by investigator-assessed conventional histopathology). The definition of DFS is the same as that of the primary endpoint of investigator-assessed DFS. Investigator-assessed in this population will be analyzed similarly to the analysis of investigator-assessed DFS in the ITT population.

Exploratory biomarker analyses will be performed in an effort to understand the association of these markers with study drug response and mechanism of action, including efficacy and/or adverse events. Biomarker analyses may be described in a separate analysis plan and summarized in a separate report.

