6.4.3 Exploratory Efficacy Endpoints

Exploratory analyses of the following primary and secondary endpoints will be performed at various timepoints (e.g., every 6 months after randomization): investigator-assessed DFS, OS, IRF-assessed DFS, IRF-assessed EFS, DSS, and DMFS. Event-free rates will be estimated by Kaplan-Meier methodology, and the 95% CI will be estimated using Greenwood's formula. The 95% CI for the difference in event-free rates between the two arms will be estimated using the normal approximation to the binomial distribution.

To assess the consistency of study results in subgroups defined by demographic and baseline characteristics, efficacy outcomes of *investigator-assessed DFS, OS, IRF-assessed DFS, IRF-assessed EFS, DSS, and DMFS* in patient subgroups will be examined. Summaries of these endpoints, including unstratified HRs estimated from the Cox proportional hazards model *and* Kaplan-Meier estimates of the median will be produced separately for each level of the subgroup.

Investigator-DFS will be summarized in patients with tumor Fuhrman Grade 4 or sarcomatoid histology (defined by investigator-assessed conventional histopathology).

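### The confidence interval for the between-arm difference in Kaplan-Meier rates rests on a binomial variance that ignores censoring, although each arm's own interval uses Greenwood's formula

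*SAP*

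**What the plan says.** SAP 5.4.8 covers the one-, two- and three-year investigator-assessed DFS rates, which are secondary endpoints. For each arm it says: "The DFS rates will be estimated by Kaplan-Meier methodology, and the 95% CI will be estimated using Greenwood's formula". Its next sentence sets the interval for the difference "between the two arms will be estimated using the normal approximation to the binomial distribution". SAP 5.4.9 carries this to the IRF-assessed rates: "DFS rate will be analyzed similarly to the analysis of one, two, and three-year investigator-assessed DFS rate".

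SAP 5.5 repeats the pair of rules for investigator-assessed DFS, OS, IRF-assessed DFS, IRF-assessed EFS, DSS and DMFS. The timepoints there are open-ended, with six-monthly spacing as the example: "The 95% CI for the difference in event-free rates between the two arms will be estimated using the normal approximation to the binomial distribution". Protocol 6.4.2 and 6.4.3 use the same pairing; for the single-arm rates, Protocol 6.4.3 reads "Event-free rates will be estimated by Kaplan-Meier methodology, and the 95% CI will be estimated using Greenwood's formula".

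Neither document brings the Greenwood variances into the interval for the difference, defines an n for the binomial formula, or says how censored patients enter it. SAP Section 6 states that there is no further supporting document.

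One more rule matters for the IRF endpoint. Under SAP 5.4.3, patients found to have baseline "disease in the 2nd Stream read will be censored at the randomization date".

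**The concern.** The binomial variance p(1-p)/n is right for a proportion when each of n patients is known to be event-free or not at time t. A Kaplan-Meier estimate is used because that is not so. Greenwood's variance accounts for the shrinking risk set and equals the binomial variance only when nobody is censored before t.

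Taken literally, the plan would print two Greenwood intervals beside an interval for their difference that does not agree with them. Its width would depend on a programming choice the SAP leaves open. With n as the arm size, censored patients count as fully observed and the interval is too narrow. With n as the number still at risk, patients who already had the event drop out of the denominator and the interval is too wide.

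The IRF-assessed rates have a second source of censoring. Patients censored at randomization add nothing to the Kaplan-Meier estimate, but an n equal to the arm size counts them in full from Year 1 onward.

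**Working it through.** **Inputs.** From SAP 3.2: 764 patients randomized 1:1 (382 per arm), median DFS 47 and 67 months, 5% loss to follow-up over 24 months, accrual over 33 months with an 8-month ramp-up, analysis at Month 67. From SAP 3.3: median OS 100 and 143 months, 2% loss over 24 months, final analysis at Month 88. Assumed here: exponential event and dropout times, and a linear ramp followed by constant accrual.

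**The plan's own figure.** The Schoenfeld formula with HR 0.70, two-sided alpha 0.05 and 90% power gives 331 events. With HR = 47/67 it gives 335, and the Freedman formula gives 338. The plan states 334. The model above projects about 328 DFS events at Month 67, 1.7% below 334, so it represents the planned censoring adequately.

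**Formulas, per arm.** S(t) is the event-free probability, h the hazard, and G(t) the probability of not being censored by t (dropout and data cutoff).

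- Greenwood (asymptotic): S(t)² × ∫₀ᵗ h / [382 × S(u) × G(u)] du
- Binomial, n = arm size: S(1-S)/382
- Binomial, n = number at risk: S(1-S)/(382 × S × G)

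The half-width for the difference is 1.96 × the square root of the two arms' summed variances. Coverage is 2Φ(1.96 × SE used / SE Greenwood) - 1.

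**Year 3 in full.** S is 2^(-36/47) = 0.588 on placebo and 2^(-36/67) = 0.689 on atezolizumab. The binomial SE is √(0.588 × 0.412/382 + 0.689 × 0.311/382) = 0.0346, a half-width of 6.78 percentage points. The Greenwood SE is 0.0353, a half-width of 6.93. The ratio is 6.78/6.93 = 0.978, about 2% too narrow.

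**Investigator-assessed DFS, n = 382 per arm, Month 67 cutoff (half-widths in percentage points):**

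| Month | At risk, placebo / atezolizumab | Binomial | Greenwood | Too narrow by | Coverage |
|---|---|---|---|---|---|
| 12 | 312 / 329 | 4.90 | 4.94 | 1% | 94.8% |
| 24 | 255 / 283 | 6.19 | 6.27 | 1% | 94.7% |
| 36 | 194 / 227 | 6.78 | 6.93 | 2% | 94.5% |
| 48 | 88 / 108 | 7.01 | 7.70 | 9% | 92.6% |
| 54 | 48 / 60 | 7.04 | 8.43 | 17% | 89.8% |
| 60 | 15 / 19 | 7.03 | 10.10 | 30% | 82.7% |

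About 10% of each arm is censored by 36 months and 31-36% by 48 months, which explains the turn after Year 3.

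**Simulation check.** In 6000 simulated trials with estimated variances, the binomial interval covered 94.3%, 92.4%, 89.2% and 83.2% of the time at 36, 48, 54 and 60 months. Summed Greenwood variances gave 94.6%, 94.8%, 94.9% and 94.6%.

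**n = number at risk.** Half-widths at Years 1, 2 and 3 are 5.36, 7.40 and 9.18 against Greenwood's 4.94, 6.27 and 6.93. The ratios are 1.085, 1.18 and 1.32.

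**IRF-assessed DFS, n = 382.** If a fraction f is censored at randomization, G is multiplied by (1 - f) and every Greenwood SE by 1/√(1 - f). The documents give no f for this trial. Protocol 3.3.6 reports that in another adjuvant trial 11% of patients judged disease-free by the investigator "were diagnosed with metastatic disease by independent radiologic review". With f = 11% the factor is 1.060, and Years 1, 2 and 3 are 6.3%, 6.9% and 7.7% too narrow (coverage 93.4%, 93.2%, 92.9%). At Year 3 the shortfall by f is:

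| f | 1% | 3% | 5% | 11% | 15% |
|---|---|---|---|---|---|
| Too narrow by | 3% | 4% | 5% | 8% | 10% |

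If n leaves out the patients censored at randomization, the shortfall returns to 1-2% for any f.

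**OS at Month 88, n = 382.** The interval is 2% too narrow at 60 months, 4% at 66 and 8% at 72.

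**The case against.** The best defence is that the wording is loose. The sentence follows directly after Kaplan-Meier and Greenwood are named, no p(1-p)/n is written out, and the authors may have meant a normal-approximation interval using the Greenwood standard errors. That is possible. But the text names the binomial distribution right after naming Greenwood, in two SAP sections and two protocol sections, and nothing links the two. Followed as written, the rule gives the wrong variance; if Greenwood was meant, the correction only records the intent.

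Several limits on size stand:

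- With n as the arm size, the error for investigator-assessed DFS is negligible at Years 1 to 3, the only timepoints the plan fixes.
- Months 48 to 60 are not named anywhere, and by Month 60 only about 15 and 19 patients remain at risk. The 30% figure describes a sparse tail and should carry little weight, although SAP 5.5 sets no upper limit on timepoints.
- Neither document proposes the number at risk as n. It shows only how far the choice could move the result.
- The 11% is borrowed. Here central review of baseline scans was an eligibility step (Protocol 4.1.1 and 4.5.5), and SAP 1.2.3.1 says that nearly all patients whose recurrence was backdated to baseline under the first charter had passed that review. The true fraction may be lower, hence the range from 1%.

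These intervals are also descriptive: the formal hierarchy in SAP 3.1 contains only investigator-assessed DFS and then OS.

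**Conclusion.** The concern holds and is minor. The stated method for the difference does not account for censoring, conflicts with the method used for each arm, and leaves n undefined. For a secondary endpoint, two programmers following the SAP could report a Year 3 half-width of 6.8 or 9.2 points where the Greenwood value is 6.9.

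Under the likeliest reading, n = 382, the error is negligible for investigator-assessed DFS through Year 3, modest for the IRF-assessed rates, and material only at late exploratory timepoints. These sizes rest on the plan's accrual, dropout and medians with exponential times; the IRF figures also rest on an assumed fraction with baseline disease. The log-rank tests, hazard ratios, single-arm intervals and type I error control are unaffected.

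**What to change.** In SAP 5.4.8 and 5.5, replace the sentence on the difference with: *The 95% CI for the difference will use a normal approximation, with standard error equal to the square root of the sum of the two arms' Greenwood variances.* SAP 5.4.9 follows by reference. Record the change in SAP Appendix 1, which now lists none.

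Protocol 6.4.2 and 6.4.3 should be aligned too. That can wait for the next amendment, because the SAP's Introduction says it supersedes the protocol for the regulatory filing.

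The cost is small: no new data, and the plan already computes both variances. Against the n = 382 reading, investigator-assessed DFS intervals widen by 1-2% at Years 1 to 3, and by about 10%, 20% and 44% at 48, 54 and 60 months if those are reported.
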